- 5.6.2.3. If EKG QTcF prior to 1st dose, or any EKG performed then after, is above 480msec a minimum of 3 sequential 12 lead EKGs, separated by at least 2 minutes, must be performed.
- 5.6.3. For the multiple EKGs which are obtained, the average of the QTcF intervals must be ≤ 480 msec before the patient is dosed. Dosing management based on QTc interval it is described in table 5.
- 5.6.4. If EKG average is ≥ 480 msec patient must have an assessment of serum potassium, magnesium, and calcium (total corrected for albumin, or ionized calcium) in order to rule out correctable electrolytes abnormalities that could potentially correct prolonged QTcF. On any day and time in which electrolytes are assessed, if the value is $< LLN$, then the patient's potassium, calcium, phosphorous or magnesium should be supplemented as per standard Moffitt procedure. After electrolytes replacement 3 sequential 12 lead EKGs, separated by at least 2 minutes, must be performed to ensure it is ≤ 480 msec to proceed.
- 5.6.5. Treatment decision to administered PANO will be made by the treating provider at Moffitt Cancer Center and will be based on QTcF as determined by the automated machine reading at the investigational site which is available in the MUSE system. All cardiac events should be treated as per the local standard of care and referred to a cardiologist if clinically indicated. Any final decisions concerning dose modifications or permanently

discontinuing the patient from study drug due to QTcF prolongation will be based on the Investigator’s clinical assessment.

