If ANY EKG performed while patient is on trial shows a QTcF \geq 480, a minimum of 3 sequential 12 lead EKGs separated by at least 2 minutes, should be performed. QTcF from single EKG or average of 3 EKG must be \leq 480 msec for the patient to be treated with PANO. Electrolyte replacement and/or avoiding drug(s) that could potentially prolonged QTcF should be attempted when indicated. PANO could be resumed once QTcF is \leq 480 as per clinical judgement of the treating physician at Moffitt Cancer Center or PI or designee. If Muse system is malfunctioning, EKG machine should provide EKG printout which provides QT correction based on Bazett's formula. In these circumstances, QTcB is allowed to be used to decide eligibility and/or PANO dosing if heart rate is equal or above 60. QTcF can also be calculated with QT and heart rate provided in printout. QTcF is obtained based on the following formula: $QT/RR^{0.33}$. $RR= 60000/Heart\ rate$. Can use web based link <http://www.thecalculator.co/health/QTc-Calculator-385.html>. or similar to avoid calculation errors.

Table 4 Cardiac assessment monitoring schedule

Day of Treatment	EKG monitoring
Screening	
1 EKG
 
If QtcF \geq 480 msec a total of 3 sequential EKGs separated by at least 2-5 minutes will be performed and the average QTcF should be less than 480 msec to be eligible.

First dose of PANO	
PRE DOSE: 1 EKG.
 
If QtcF \geq 480 msec a total of 3 sequential EKGs separated by at least 2-5 minutes will be performed and the average QTcF should be less than 480 msec to proceed. Check correctable electrolytes abnormalities (section 5.6.4), replace and repeat 3EKG to ensure Qtc\leq 479 to proceed.
 
POST DOSE: should be performed at 3 hours \pm 0.5 hour. Perform 1 EKG. If QtcF \geq 480 msec then performed 3 EKGs at least 2-5 minutes. If average QTcF \geq 480 msec or 60 msec above baseline, dosing should be held including follow-up triplicate ECGs and correction of electrolyte abnormalities should be performed to proceed with dose number 2 of PANO.

Day of Treatment	EKG monitoring
Third dose of PANO	PRE DOSE: 1 EKG. If QtcF \geq 480 msec a total of 3 sequential EKGs separated by at least 2-5 minutes will be performed and the average QTcF should be less than 480 msec to proceed. Check correctable electrolytes abnormalities (section 5.6.4), replace and repeat 3EKG to ensure bellow QtcF \leq 479 to proceed.

Table 5: Treatment decision based on EKGs findings:

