[figure not shown]
Time Point	Average QTcF*	Action
Pre-dose before first dose	\geq 480 msec (if 1 EKG more than 480 obtain a total of 3 sequential EKGs separated by at least 2-5 minutes to calculate the average)	Delay treatment and correct any electrolyte abnormal values ** and repeat 3 EKG. If after electrolyte replacement QTcF remains \geq 480 msec, do not dose and patient is not eligible
	Above 500 msec	Patient is not eligible
Pre-dose before third dose	\geq 480 msec or above 60 msec from baseline (last EKG average at time of first dose)	Delay treatment Correct any electrolyte abnormal values ** and repeat 3 EKG. If after electrolyte replacement QTcF remains \geq 480 msec, do not dose patient. PANO could be resume if QTcF is \leq 480 as per clinical judgement of the treating physician at Moffitt Cancer Center or PI or designee before subsequent doses.
	Above 500 msec	Do NOT dose patient. Correct any electrolyte abnormal values** and repeat 3 EKGs. PANO could be resume if QTcF is \leq 480 as per clinical judgement of the treating physician at Moffitt Cancer Center or PI or designee before subsequent doses.

*QTcF: Heart rate corrected QT interval using the Fredericia formula:
 $QTc = QT / RR^{0.33}$ as per automated machine available in MUSE system or
 calculated manually (see 5.6.7).
 **: serum potassium, magnesium, calcium

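### The manual QTcF formula in Section 5.6 takes RR in milliseconds, so its result is about 9.8 times too small for the 480 and 500 msec limits

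*Combined protocol and SAP*

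**What the plan says.** Section 5.6.5 makes the automated reading the default: the decision to give panobinostat "will be based on QTcF as determined by the automated machine reading at the investigational site". An unnumbered paragraph after 5.6.5, just before Table 4, covers a MUSE malfunction and leaves three routes.

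- The printed Bazett value: "QTcB is allowed to be used to decide eligibility and/or PANO dosing if heart rate is equal or above 60".
- A hand calculation: "QTcF can also be calculated with QT and heart rate provided in printout". The formula follows: "QTcF is obtained based on the following formula: $QT/RR^{0.33}$. $RR= 60000/Heart" rate.
- A web calculator, offered as an option, "or similar to avoid calculation errors".

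The Table 5 footnote describes QTcF as "Heart rate corrected QT interval using the Fredericia formula", repeats QT/RR^0.33 and allows manual calculation. It gives no unit for RR. It sends the reader to a Section 5.6.7, a number that does not appear in the text available to us; the unnumbered paragraph may be that section.

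The result is compared with limits on the ordinary msec scale:

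- 480 msec for eligibility (Sections 4.2.9.3 and 5.6.1) and for dosing (5.6.3, Tables 4 and 5).
- 500 msec in Table 5.
- A rise from baseline. Table 4 says that after the first dose, at "480 msec or 60 msec above baseline, dosing should be held". Table 5 uses a reading "above 60 msec from baseline (last EKG average at time of first dose") before the third dose.

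**The concern.** At 60 bpm the RR interval is one second and a heart-rate correction should leave QT unchanged. With RR entered as 1000, the written formula instead divides QT by almost ten. The text supplies no later step that would restore the scale.

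The value feeds a safety gate. It decides whether a patient may enter, whether a dose may be given and whether dosing is held. The drug has a documented QT signal: Table 3 reports 27 of 666 patients with a rise above 60 msec and 6 of 666 above 500 msec, at oral doses of 20 to 60 mg. This trial gives 5 mg, so its own rates may be lower. It does, however, allow voriconazole and posaconazole (Section 5.4), while Section 5.5.1.1 asks that CYP3A4 inhibitors be avoided because they may raise panobinostat exposure. A fallback formula that passes everyone would defeat the check in the situation for which it was written.

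**Working it through.** **Inputs.** The formula and the definition of RR come from the malfunction paragraph in Section 5.6. The limits come from Section 5.6 and Tables 4 and 5. QT is taken in msec, because the limits are. This is an assumption, since no unit is given; QT in seconds would make the result smaller still. The protocol gives no worked QTcF value to reproduce.

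**Formulas**

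- As written: QT / (60000/HR)^0.33
- RR in seconds: QT / (60/HR)^0.33
- Ratio of the second to the first: 1000^0.33 = 9.77, the same at every heart rate.

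Using 0.33 in place of 1/3 changes the result by about 0.2% or less between 45 and 120 bpm and is not the problem.

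**Examples**

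| QT (msec) | HR (bpm) | As written | RR in seconds |
|---|---|---|---|
| 560 | 45 | 52.1 | 509.3 |
| 540 | 50 | 52.0 | 508.5 |
| 500 | 55 | 49.7 | 485.8 |
| 500 | 60 | 51.2 | 500.0 |
| 440 | 80 | 49.5 | 483.8 |

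All five patients are above 480 msec on the correct scale, and none is flagged as written.

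**Can the written formula ever reach 480?** The QT needed is 480 × (60000/HR)^0.33.

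| HR (bpm) | QT needed (msec) | RR interval (msec) |
|---|---|---|
| 45 | 5158 | 1333 |
| 60 | 4691 | 1000 |
| 120 | 3732 | 500 |

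In each case the QT would have to be several times longer than the whole cardiac cycle, so the 480 and 500 limits cannot be triggered.

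**The 60 msec rise.** Take QT going from 430 to 510 msec at 50 bpm.

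- Correct: 404.9 to 480.2, a rise of 75.3 msec, which should hold the dose.
- As written, both readings manual: 41.4 to 49.1, a rise of 7.7.
- For the written formula to show a rise of 60 at 50 bpm, QT would have to lengthen by 60 × (60000/50)^0.33 = 623 msec.
- Automated baseline, manual second reading: an apparent fall of 404.9 − 49.1 = 355.8 msec.

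**Where the fallback is thinnest.** Below 60 bpm the Bazett route is closed, so the hand formula or the optional calculator is all the text leaves. A correct QTcF of 480 corresponds to these printed QT values, and reads 49.1 as written in every case:

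| HR (bpm) | 45 | 50 | 55 | 59 |
|---|---|---|---|---|
| Printed QT (msec) | 528 | 510 | 494 | 483 |

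**The case against.** The strongest reply is that the error reveals itself. The formula returns about 40 to 55 for normal and prolonged readings alike, and a clinician comparing 50 with a limit of 480 would see that the units are wrong. The Fridericia correction is named, the limits are in msec, and the text that follows offers a calculator. The route is permissive and needs a MUSE outage, and Section 5.6.5 leaves final decisions on dose modification and permanent discontinuation for QTcF prolongation to the investigator's clinical assessment. At 60 bpm or above the Bazett value is allowed and is at least as large as the Fridericia value, so that fallback is conservative. Below 60 bpm any QTcF of 480 requires a printed QT above 480, which the reader has in hand.

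All of this stands, and it limits how often the error could cause harm. It does not make the formula right. The calculator is optional. Above 60 bpm the raw QT gives no such warning: 440 msec at 80 bpm looks acceptable but corrects to 484. The paragraph also does not say which value governs if a printed Bazett figure and a hand-calculated QTcF disagree.

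Two qualifications are fair. The 45 bpm floor in Section 4.2.9.2 is an enrolment exclusion; Section 5.6 sets no heart-rate floor for later doses. And because the Table 5 footnote points to a section number we cannot see, the statement that no unit is given applies to the text available.

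**Conclusion.** The concern holds. As written, the manual formula understates QTcF by a factor of 9.77 at every heart rate and cannot flag a patient against 480 or 500 msec, nor against the 60 msec rise when both readings are manual. The conclusion assumes that QT is entered in msec and that the instruction is followed literally. It should be corrected because it is an instruction for an eligibility and dosing safety check. Likely practical impact is small, since it takes an automated-system outage, no use of the calculator and acceptance of an implausible result. The sample size, the toxicity stopping rule and the analysis of the primary and secondary endpoints do not depend on it.

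**What to change.** In the malfunction paragraph of Section 5.6, define RR as 60/heart rate in seconds (equivalently, RR in msec divided by 1000) and state that QT is in msec. Add one worked example: QT 440 msec at 80 bpm gives RR = 0.75 s and QTcF = 440/0.75^0.33 = 484 msec. State the same units in the Table 5 footnote, and point its cross-reference to the paragraph that carries the formula. The limits, the Bazett route and the calculator option can stay as they are.

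This is a one-line correction with no change to visits, assessments or analysis. Section 11.5 requires a written amendment, with review by the drug supplier and the IRB, for any non-administrative change. If the correction is not classed as administrative, that review is its only cost, and it could be combined with another amendment.

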5.7. GVHD prophylaxis

We will test the combination of TAC and SIR, a combination that has proven to be safe and effective for GVHD prevention in matched allogeneic transplants (related or unrelated) in addition to PANO. We propose to test the hypothesis that this combination not only enhances T regulatory development but may modulate host-donor antigen presentation to allow an immune-tolerant microenvironment to prevent GVHD. Therefore, PANO will be initiated prior to stem cell infusion (see Appendix G) and continued for 26 weeks as shown in Figure 4:

Figure 4. GVHD prophylaxis plan.

5.7.1. Standard GVHD prophylaxis regimen:

5.7.1.1 Tacrolimus(TAC)

- 5.7.1.1.1. Tacrolimus will be administered starting on day -3 and following our institutional guidelines for dosing.
- 5.7.1.1.2. Micafungin will be used for primary fungal prophylaxis, given its minimal interaction with TAC and SIR metabolism; there will be no dose adjustment made of TAC or SIR with Micafungin as fungal prophylaxis. In those patients with active fungal infection, anti-fungal treatment will be changed to Voriconazole or Posaconazole. Additionally, those patients on corticosteroid treatment (cumulative dose of greater than or equal to 0.5 mg/kg/day) will be treated with Voriconazole or Posaconazole. In those patients on Voriconazole or Posaconazole, TAC dose will be decreased by 50-67% of its original dose and further adjusted based on serum levels.
- 5.7.1.1.3. Thrombotic microangiopathy (TMA) will be graded for severity according to CTC version 4. No changes in TAC dose will be made for TMA of grades 1 or 2. For grade 3 TMA, TAC dose will be reduced by 50%. For grade 4 TMA, TAC will be discontinued.

5.7.1.2. Sirolimus (SIR)

SIR will be administered starting on day -1 and thereafter, dosing will be adjusted to maintain therapeutic targets per our institutional standards.

SIR levels should be monitored on days 0, 2, and at least once weekly thereafter until on stable oral dose and schedule. Dose adjustments should be made according to drug levels per standard practice guidelines.

5.7.1.3 Investigational therapy: Panobinostat (PANO)

- 5.7.3.1 Patients will be treated with PANO 5 MG PO TIW (3 doses about 48 hours apart in a 7 day period) QW for 26 weeks starting prior to stem cell infusion (see Appendix G) Patient follow up will be for a total of 365 ± 30 days from initiation of the drug. During the study, PANO will be administered orally as once daily dose. Patients should receive their once-a-day oral dose of PANO approximately at the same time each day in AM or PM

(preferable PM). Each dose of PANO should be taken with about 8 oz / 240 ml glass of water. Patients should be instructed to swallow the capsules whole and not chew them. Patients must avoid grapefruit or grapefruit juice and seville (sour) oranges during the entire study.

5.7.3.2 PANO will be provided by Novartis. Oral PANO will be supplied as 5-mg pink gelatin capsules. Medication labels will comply with US legal requirements and be printed in English. They will supply no information about the patient. The storage conditions for study drug will be described on the medication label.

5.7.3.3 If the patient cannot take Panobinostat due to mucositis and/or HCT related GI toxicities (nausea/vomit/diarrhea), then he/she should take PANO on that same day within 16 hours after the missed dose if possible. After more than 16 hours, that day's dose should be withheld, and the patient should wait to take PANO until the next scheduled treatment day (i.e., patients should be instructed not to try to make-up the missed dose after 16 hours). (In our prior experience majority of patients with mucositis and/or GI toxicities were able to complete SIR PO as specified in protocol⁴).

5.7.3.4 The investigator should instruct the patient to take the study drug exactly as prescribed (promote compliance). Pill diary to help adhere with compliance is highly recommended to record actual drug compliance and will be provided to patients. All dosages prescribed and dispensed to the patient and all dose changes during the study should be recorded in pharmacy chart.

5.7.3.5 Patients will receive the planned treatment with PO PANO until they experience unacceptable toxicity that precludes further treatment (as specified in section 9).

5.7.3.6 If they develop GVHD and requires treatment with high dose corticosteroids (1-2MG/Kg) as defined in section 6 they should stop PANO as determined in section 6.3.

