2.2. Secondary Objectives

- 2.2.1. Clinical objectives:
 - 2.2.1.1. Cumulative incidence of chronic GVHD
 - 2.2.1.2. Engraftment, relapse, non-relapse mortality, overall and relapse-free survival at one year.
- 2.2.2. Biological studies to test the pharmacodynamics of TAC/SIR/PANO combination for GVHD prevention:
 - 2.2.2.1. Immune Reconstitution determined by flow cytometry
 - 2.2.2.2. Histone acetylation of T cells and DC subsets by Western Blot and flow cytometry
 - 2.2.2.3. T reg immune-reconstitution, Foxp3+ expression and acetylation by flow cytometry
 - 2.2.2.4. Inflammatory cytokine and Biomarker expression profiling
 - 2.2.2.5. Stat-3 activation and acetylation
 - 2.2.2.6. Panobinostat pharmacokinetics

	Objective	Endpoint
Primary Clinical Objectives	Prospectively determine the cumulative incidence of acute GVHD grades 2-4 using TAC and SIR in addition to PANO for GVHD prevention. Study parameters: We will consider $\geq 43\%$ incidence of grade II-IV aGVHD not acceptable. We will use 23% incidence rate of GVHD as target.	GVHD severity stage and grading and distribution will be measured weekly from day of transplant to day 90 +/- 14 using standard scoring system. Stage of GVHD will be given for each site of involvement (e.g. skin, liver, and gut), as well as a composite score for overall acute GVHD grade. Pathologic confirmation of aGVHD will be dictated by usual clinical practice, and not

		mandated by this protocol. Treatment of GVHD will not be mandated.
Secondary Clinical Objectives	Cumulative incidence of chronic GVHD	GVHD with onset after 100 days post-HCT with presence of at least one diagnostic manifestation of chronic c-GVHD or distinct manifestation confirmed by biopsy or other relevant tests (eg PFT). Classified as: 1- Classic chronic GVHD - meets criteria for chronic GVHD and has no features consistent with aGVHD or 2- Overlap syndrome - features of acute and chronic GVHD exist together. C-GVHD will be measured prospectively in all patients on days 90+/-14 , 120 +/- 14, 150 +/- 14, 180+/- 14, 270+/- 30, and 365 +/- 30 as per standardized scoring system.
	Engraftment	Stable engraftment for WBC is defined as a sustained absolute neutrophil count > 500 over 3 days without cytokine support. Stable platelet engraftments is defined as count of > 20,000 over 7 days without transfusion support. Time to engraftment is defined as time from day 0 to day of sustained engraftment per above criteria for both platelets and WBC.

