	Cumulative incidence of relapse/progression and non-relapse mortality at one year. Overall Survival and	Incidence of primary disease relapse and non-relapse related death will be reported per standard definitions. These will be treated as competing risk events. Non-

	
Relapse-free Survival at one year.
	
relapse death is defined as death in continuous remission from primary disease requiring transplantation. Survival outcomes: Overall survival: Time from transplant date to death from any cause. Relapse-free survival: Time from transplant date to death or primary disease relapse.

Secondary Exploratory Objectives
	
Biologic studies (appendix F)to test thepharmacodynamics of TAC/SIR/PANO combination for GVHD prevention. Results will be compared with compared to data from similar external control patients treated with an identical protocol except for PANO
	
T Cells, especially T regs, immune-reconstitution, will be measured to assess whether PANO increased amounts of Treg cells post HCT.
 
Histone acetylation of T cells, T regs and DC subsets will be measured to test the activity of PANO as an inhibitor of histone deacetylases on targeted specific cell subsets.
 
Inflammatory cytokine will be measure to assess whether PANO contribute to generate an immune-modulatory cytokine micro-enviroment decreasing the production of pro-inflammatory cytokines .
 
Biomarker expression profiling will be measured to assess correlation with GVHD clinical outcome.
 
Stat-3 activation and acetylation will be measured in cells subsets to test the activity of PANO as an inhibitor of histone deacetylases

3. Overall study design

- 3.1. **This study will test PANO in combination with TAC/SIR for acute GVHD prevention.** This is a Phase II, single arm, non-randomized study and does not contain a treatment control group. This Phase II study will assess whether TAC/SIR/PANO provides potential efficacy for GVHD prevention, and whether results hold sufficient promise for definitive testing of PANO in subsequent randomized clinical trials and/or TAC de-escalation studies. Correlative studies results ONLY will be compared to an “external control” patient subset that will be treated with TAC/SIR with same inclusion and exclusion criteria as this protocol except that they will not be treated with PANO.
- 3.2. **Site(s):** Protocol will be performed at Moffitt Cancer Center.

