- 3.3. **Sample Size and accrual rate.** It is estimated that 2 patients will be entered into the treatment study each month, therefore, we anticipate 24 months for completion of the study that will require **n=44** total patients for the treatment arm. We are planning to enroll **n=20** patients for “external control patients”. We anticipate 0.5 patients/month for “external control” subjects and accrual will happen concomitant to treatment arm patients. Therefore a total of **64** subjects will be accrued in total including treatment arm and external control.
- 3.4. **Patient Follow up.** Patients will be evaluated weekly from day of transplant until day 100 to measure acute GVHD using standard scoring system (defined in Appendix A). Stage of GVHD will be assessed for each site of involvement (e.g. skin, liver, and gut), as well as a composite score for overall acute GVHD grade determined. Pathologic confirmation of aGVHD will be dictated by usual clinical practice. Patient will be followed on days +90 +/-14, 120 +/- 14, 150 +/- 14, 180+/- 14, 270+/-30, and 360 +/- 30 for chronic-GVHD assessment and adverse events toxicity assessment. Taper of immunosuppression is suggested- not mandatory and treatment of GVHD is not mandated (section 6.2-6.3).
- 3.5. **Withdrawal.** from the study will take place under the following circumstances: those patients who sign consent for the study, but fail to initiate treatment due to:
- 3.5.1. denial of coverage from insurance provider
 - 3.5.2. disease progression prior to initiation of treatment
 - 3.5.3. death prior to initiation of treatment
 - 3.5.4. withdrawal of patient consent at any time after therapy

4. Patient Population: Inclusion and Exclusion criteria

- 4.1. **Inclusion Criteria:**
- 4.1.1. Male or female

- 4.1.2. Age \geq 18 years or older at time of enrollment
 - 4.1.3. Signed informed consent
 - 4.1.4. Hematologic disorder requiring allogeneic hematopoietic cell transplantation
 - 4.1.5. LVEF \geq 45% by MUGA scan or echocardiogram
 - 4.1.6. FEV1, FVC, and DLCO adjusted \geq 50% of predicted values on pulmonary function tests
 - 4.1.7. Transaminases (AST, ALT) $<$ 3 times upper limit of normal values
 - 4.1.8. Creatinine clearance calculated \geq 50mL/min
 - 4.1.9. Karnofsky Performance Status Score \geq 60%.
 - 4.1.10. HLA matched 8/8 (A, B, C, DRB1) related or unrelated donor
- 4.2. **Exclusion Criteria:**
- 4.2.1. Active infection not controlled with appropriate antimicrobial therapy

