- 8.7. For patients that PANO is discontinued due to GVHD they are allowed to continue to be ON study. All assessment, procedures, CRF forms, correlative studies (appendix F) will be performed identically to patients that continue to take PANO and we will not deviate from what is stipulated in the protocol for patients that are receiving study drug on study.
- 8.8. Special considerations for toxicity observed up to day +7 post transplant: Due to unknown interactions between conditioning regimen and PANO, guidance is provided between PANO 1st dose to day +7 HCT as follows:
 - 8.8.1. PANO will be stopped for any non-hematological CTCAE (v4) grade 3 or higher toxicities unexpected for HCT (see table 8) seen between first dose of study drug and day +7 post-HCT. If there is complete reversal of toxicity, PANO can be resumed after 7 days and a minimum of one week off study drug and continued until completion of protocol-specified dosing schedule. In the absence of complete reversal of toxicity within 7 days, the study drug will be discontinued and the patient removed from the study. All such patients will remain evaluable for analysis and not replaced.

8.9. For gastrointestinal (GI) symptoms (diarrhea or nausea/vomiting) thought to be related to PANO from day -5/-6 to day +7 and/or after recovery from acute GI toxicity due to chemotherapy: The PANO dose may be modified according to the severity of the GI side effects as suggested and described in Table 6 and 7. Depending on the patients' clinical status, dose adjustments may be made within 1 week from when the lab work is completed. Patients who require PANO adjustment will have their dose HOLD for 3 doses and may resume 100% dosing thereafter at physician discretion. A trial of anti-emetics and anti-motility agents should be considered (institutional Clinical Practice Guidelines) before modifying the dose of PANO. In case patient regurgitate PANO pill will be allowed to re-dose after anti-emetics trial. PANO should continue for patients who develop GI symptoms related to infection.

Table 6. Management guidance for Diarrhea.

	Diarrhea Grade	PANO dose reduction
Mild	Grade 1: <4 stools/day over baseline	0%
Moderate	Grade 2: Increase 4-6 stools/day over baseline	0%
Severe	Grade 3: Increase >7 stools/day over baseline	No GI GVHD: hold only after failure of antimotility agents. Resume once the GI toxicity has resolved to grade 0-2 and continued until completion of protocol-specified dosing schedule If GI GVHD*

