Toxicity will be assessed using the NIH-NCI Common Terminology Criteria for Adverse Events, version(CTCAE) version 4.0 (v.4) (http://evs.nci.nih.gov/ftp1/CTCAE/CTCAE_4.03_2010-06-14_QuickReference_5x7.pdf).

9.2. AE reporting:

- 9.2.1. All non-hematological toxicities unexpected with HCT will be reported from the first day PANO is administered until day 180±7 days unless specified otherwise in the protocol. After day 180±7 post HCT subjects will only be followed only for GVHD, relapse and survival until day 365±30.
- 9.2.2. Information about relevant AE unexpected to HCT, whether volunteered by the subject, discovered by investigator questioning, or detected through physical examination, laboratory test or other means, will be collected and recorded. AE should be followed as

appropriate for at least 14 days following the last dose of PANO. All AE should be treated appropriately. Such treatment may include changes in study drug treatment including possible interruption or discontinuation, starting or stopping concomitant treatments, changes in the frequency or nature of assessments, hospitalization, or any other medically required intervention.

- 9.2.3. As far as “possible or definitive” related AE unexpected to HCT, each adverse event should be evaluated to determine:
 - 9.2.3.1. the severity grade (mild, moderate, severe) or (grade 1-4)
 - 9.2.3.2. its relationship to the study drug(s) (suspected/not suspected)
 - 9.2.3.3. its duration (start and end dates or if continuing at final exam)
 - 9.2.3.4. action taken (no action taken; study drug dosage adjusted/temporarily interrupted; study drug permanently discontinued due to this adverse event; concomitant medication taken; non-drug therapy given; hospitalization/prolonged hospitalization)
 - 9.2.3.5. whether it constitutes a serious adverse event (SAE).

- 9.3. **SAE is an undesirable sign**, symptom or medical condition which:
 - 9.3.1. Is fatal or life-threatening
 - 9.3.2. Results in persistent or significant disability/incapacity
 - 9.3.3. Constitutes a congenital anomaly/birth defect
 - 9.3.4. Is medically significant, i.e., defined as an event that jeopardizes the patient or may require medical or surgical intervention to prevent one of the outcomes listed above
 - 9.3.5. Requires inpatient hospitalization or prolongation of existing hospitalization
 - 9.3.6. Note that hospitalizations for the following reasons should not be reported as serious adverse events:

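### The protocol gives three different ends of follow-up for outcomes wanted at one year after transplant, and none requires status to be confirmed at or after day 365

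*Combined protocol and SAP*

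**What the plan says.** Section 2.2.1.2 lists among the secondary objectives "relapse, non-relapse mortality, overall and relapse-free survival at one year". The objective and endpoint table in section 2.2 defines overall survival as "Time from transplant date to death from any cause" and gives relapse-free survival the same starting point. Section 12.5 repeats the transplant origin for both and analyses them by Kaplan-Meier. Relapse and non-relapse mortality are analysed by cumulative incidence. No origin is stated for those two, but transplant is implied.

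The end of follow-up is given in several places:

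- Section 5.7.3.1 (panobinostat administration): "Patient follow up will be for a total of 365 ± 30 days from initiation of the drug". Section 8.9 refers to the period "from day -5/-6 to day +7". Appendix G shows the first dose on day -6 in one busulfan/fludarabine calendar and on day -5 in the others.
- Section 3.4: visits at days "270+/-30, and 360 +/- 30 for chronic-GVHD assessment" and for toxicity.
- Section 9.2.1: after day 180, "subjects will only be followed only for GVHD, relapse and survival until day 365±30", in a sentence that counts days post HCT.
- The endpoint table in section 2.2 (chronic GVHD) and the Appendix C calendar: day 365 ± 30 on the transplant scale.

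No section requires vital or relapse status at or after day 365 from transplant. None says how a patient last seen before day 365 enters the one-year estimates.

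**The concern.** The endpoint clock starts at transplant, while one of the follow-up clocks starts five or six days earlier, so a patient can complete that follow-up on its nominal day without reaching one year. The ±30-day window is a larger matter than the offset: even when counted from transplant, it lets an on-time last contact fall up to 30 days short. A survivor censored there contributes nothing at day 365, and a relapse or death between last contact and day 365 may go unrecorded. At stake is the number of patients supporting the one-year figures. There is also a conflict between sections that staff would have to resolve patient by patient, and that cannot be fully repaired once patients have left follow-up.

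**Working it through.** The plan states no power, precision or number at risk for the one-year outcomes, so there is no figure of its own to reproduce.

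**Step 1: put each rule on the transplant scale.** Last contact = 365 ± 30 plus the day of first dose, where the clock is drug start.

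| Source | Nominal day | Window |
|---|---|---|
| 5.7.3.1, first dose day -5 | 365 − 5 = 360 | 330-390 |
| 5.7.3.1, first dose day -6 | 365 − 6 = 359 | 329-389 |
| 3.4 (chronic GVHD, toxicity) | 360 | 330-390 |
| 9.2.1, endpoint table, Appendix C | 365 | 335-395 |

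**Step 2: share of last contacts at or after day 365.** The documents do not say how contacts fall within the window. If they are uniform, the share is (window end − 365)/60.

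- 5.7.3.1: (390 − 365)/60 = 41.7% or (389 − 365)/60 = 40.0%, so 58-60% fall short.
- Day 365 ± 30 from transplant: (395 − 365)/60 = 50%, so 50% fall short.

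Sensitivity: if contacts cluster normally around the nominal day of 5.7.3.1 with SD 5 to 15 days, the share reaching day 365 runs from P(Z ≥ 6/5) = 12% to P(Z ≥ 5/15) = 37%.

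**Step 3: number at risk at day 365.** Take 44 patients (section 12.1) and an assumed one-year survival S of 60% or 75%. At risk = 44 × S × share.

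- Status known for all survivors: 44 × 0.60 = 26.4; 44 × 0.75 = 33.0.
- 5.7.3.1: 26.4 × 0.40 = 10.6 to 26.4 × 0.417 = 11.0; 33.0 × 0.40 = 13.2 to 33.0 × 0.417 = 13.8.
- Transplant scale: 26.4 × 0.50 = 13.2; 33.0 × 0.50 = 16.5.

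So about 11-17 patients, against 26-33.

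**Step 4: precision.** Greenwood's large-sample variance is S² ∫ λ/(N·S(t)·G(t)) dt from 0 to 365, with exponential survival (hazard λ) and G(t) the share still under follow-up at t. For N = 44 and S = 0.60:

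- Full ascertainment: √(0.60 × 0.40/44) = 0.0739.
- 5.7.3.1: 0.0761-0.0762, a ratio of about 1.03.
- Transplant scale: 0.0753, a ratio of about 1.02.

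Across S = 50-80%, the standard error is 0.060-0.075 with full ascertainment and 0.062-0.078 under 5.7.3.1.

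**Step 5: unseen deaths.** With uniform censoring from day 329.5 (midway between the two 5.7.3.1 windows), expected deaths after last contact but before day 365 are about 44 × λ × S(t) × (35.5²/120), where 35.5²/120 = 10.5.

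- S = 0.60: λ = 0.511/365 = 0.00140 and S(t) ≈ 0.61, giving 0.39.
- S = 0.75: λ = 0.288/365 = 0.00079 and S(t) ≈ 0.76, giving 0.28.

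**The case against.** The drug-start sentence sits in a section on drug administration. Section 9.2.1, which governs follow-up for relapse and survival, counts from transplant and places the nominal end exactly at day 365; the endpoint table and Appendix C agree. Section 3.4's day-360 visit is for chronic GVHD and toxicity, and chronic GVHD has no stated one-year time point. Kaplan-Meier and cumulative-incidence methods accommodate censoring. Section 12.5 calls the secondary endpoints exploratory, and no decision rule uses them.

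All of this stands, and it limits the point to a conflict between sections with a small statistical cost. It does not remove the point. The ±30-day window in section 9.2.1 still allows an on-schedule last contact as early as day 335, and nothing requires a later check.

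A reader might infer that most patients cannot reach one year. The documents do not support that: every window runs to day 389-395, and any majority falling short depends on an assumed pattern of contacts. A reader might also infer that the curves stop before one year with nobody at risk at day 365. That would need every survivor to be last seen on the nominal day under the earlier of the rules, and censored there.

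**Conclusion.** The point holds as an inconsistency with a modest effect. Overall and relapse-free survival explicitly run from transplant, and relapse and non-relapse mortality do so by implication. The sections give nominal ends of day 359-360, 360 and 365, and the stated windows allow on-schedule survivors to be censored before the time point that the endpoints name. The consequence is thinner support at day 365, slightly wider intervals and less than one unseen death expected. It is not an unusable or materially biased estimate. The sizes rest on uniform last contacts, exponential survival, one-year survival of 60-75% and 44 treated patients; of these only the 44 comes from the protocol. The day-100 acute GVHD decision in section 12.1 is untouched. The change is worth making because it costs little and affects what is collected on four named one-year outcomes.

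**What to change.** Count follow-up from transplant (day 0) in sections 5.7.3.1, 3.4 and 9.2.1, and state that origin explicitly in Appendix C, with the same nominal final day in each. Require vital and relapse status to be confirmed at or after day 365 post-transplant. Two ways would serve equally well: set the final window at day 365 to 395, or keep the ±30-day visit and add a status check at or after day 365. State in section 12.5 that relapse and non-relapse mortality are also timed from transplant, and that the one-year analysis is run once the last treated patient has passed day 365.

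The cost is a wording amendment and some final contacts a few weeks later. The first option adds no visit; the second adds only a status check. Changing the origin alone would not be enough: under uniform contact it raises the share reaching day 365 only from 40-42% to 50%.
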